4.1 Inclusion Criteria

All the following criteria must be met for a subject to be enrolled in this trial:

1. Adult males and non-pregnant females between 18 years and 60 years of age inclusive.
2. General good health, without significant medical illness, physical examination findings, or significant laboratory abnormalities as determined by the investigator.
3. Available for the duration of the trial.

4. Able to demonstrate understanding of key study concepts, study rationale, and study participation requirements by scoring $\geq 70\%$ on a written comprehension assessment in ≤ 3 attempts.
5. Willingness to participate in the study as evidenced by signing the informed consent document.
6. Willingness to allow storage and testing of laboratory samples for future research.
7. Received 2 doses of live attenuated H2N2, H6N1, or H9N2 vaccine in a prior trial (Cohort 1) or H2N2, H6N1 and H9N2 naïve (Cohort 2)
8. Willingness to forego seasonal influenza virus vaccination from 1 month before vaccination until 3 months after vaccination.
9. Female subjects of childbearing potential must agree to have used effective birth control methods beginning at least one month prior to vaccination, and continuing with ‘per label/fully effective use’ for the chosen method for duration of the study, from amongst these:
 - pharmacologic/hormonal contraceptives, including oral, parenteral, subcutaneous, and transcutaneous delivery;
 - condoms with spermicide;
 - diaphragm with spermicide;
 - intrauterine device;
 - absolute abstinence from heterosexual intercourse as a matter of normal preferred lifestyle;

or must be surgically sterile or must be age 50 AND have had no menses at all for at least one full year.

All females must provide urine for pregnancy testing prior to enrollment (immediately prior vaccination), as well as a statement of menstrual history and a summary of all potentially reproductive sexual activity for the month prior to vaccination, and at each study contact throughout the study, and report known or suspected pregnancy immediately.

10. Willingness to refrain from blood donation during the course of the study.

4.2 Exclusion Criteria

The presence of any one of the following criteria is sufficient to exclude a prospective subject from enrolling in this study:

1. Pregnancy as determined by a positive test for human chorionic gonadotropin (β -HCG), an indicator of pregnancy or history of recent unprotected intercourse in a woman of reproductive capacity.
2. Currently breast-feeding.
3. Evidence of clinically significant neurologic, cardiac, pulmonary, hematologic, hepatic, rheumatologic, autoimmune, or renal disease by history, physical examination, and/or laboratory studies.
4. Behavioral or cognitive impairment or psychiatric disease that in the opinion of the investigator affects the ability of the subject to understand and cooperate with the study protocol.

5. Have medical, occupational, or family problems as a result of alcohol or illicit drug use during the past 12 months.
6. Other condition that in the opinion of the investigator would jeopardize the safety or rights of a subject participating in the trial or would render the subject unable to comply with the protocol.
7. History of anaphylaxis in response to any vaccine or vaccine component.
8. History of life-threatening reaction to prior influenza vaccine.
9. Positive enzyme-linked immunosorbent assay (ELISA) and confirmatory test for human immunodeficiency virus type 1 (HIV-1).
10. Positive ELISA and confirmatory test (e.g., HCV RNA PCR) for hepatitis C virus (HCV).
11. Positive hepatitis B virus surface antigen (HBsAg) by ELISA.
12. Known immunodeficiency syndrome or history suggestive of impaired immune function.
13. History of Guillain-Barré syndrome.
14. Use of chronic oral or intravenous administration (≥ 14 days) of immunosuppressive doses of steroids, i.e., prednisone >10 mg per day, immunosuppressants or other immune-modifying drugs within 30 days of starting this study.
15. Receipt of a live vaccine within 4 weeks or a killed vaccine within 2 weeks prior to study vaccination.
16. Receipt of blood or blood-derived products (including immunoglobulin) within 6 months prior to study vaccination.
17. Receipt of another investigational vaccine or drug within 30 days prior to study vaccination.

In addition to the above, participants in Cohort 1 (pLAI^V recipients) and Cohort 2 (naïve cohort) must also not experience any of the following:

1. Previous enrollment in an H5N1 influenza vaccine trial.

Participants in Cohort 2 (naïve cohort) will be excluded if they are:

1. Seropositive to the H5N1 influenza A virus (serum hemagglutination inhibition assay (HAI) titer $>1:8$).
2. Have previously received an investigational LAIV in another study.

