6.2 Recruitment

The CIR disseminates information about opportunities to participate in its vaccine clinical trials via IRB-approved content on its own website (centerforimmunizationresearch.org), social media platforms, YouTube, and in web, newspaper, radio and television advertisements. Study specific IRB-approved fliers and brochures are distributed locally.

Cohort 1 will consist of prior recipients of Live Attenuated H2N2, H6N1 and H9N2 Influenza Vaccines as participants in previous CIR studies (CIR 211, CIR 247, CIR 251). With each initial and subsequent telephone contact, subjects are asked if they will allow us to call them about opportunities to participate in future studies. The response to this question is documented on a pre-screening assessment form and in the CIR Adult Studies Data Base. Study staff has compiled a list of approximately 63 volunteers who participated in these three studies from 2005 - 2009. They will be contacted via phone, and/or IRB-approved letter, and invited to participate in our general screening study to see if they would be eligible and willing to participate in this study as recalled subjects. After this initial contact, subjects will be referred to the telephone recruiter. The recruiter will administer a brief qualifying phone screen after obtaining verbal consent and eligible recruits will be scheduled for in-person screening visits according to their interests and availability.

Cohort 2 – the control cohort consisting of LAIV-naïve/H5 antibody negative subjects, will be identified as individuals who make inquiries by telephone call or email to the clinical trial site. A telephone recruiter will respond to calls and emails and provide brief scripted descriptions of currently accruing CIR trials as specified in the CIR’s general screening protocol. The recruiter will administer a brief qualifying phone screen after obtaining verbal consent and eligible recruits will be scheduled for in-person screening visits according to their interests and availability.

The screening evaluation outlined below will be completed within 60 days prior to vaccination. During the initial in-person screening visit trained study staff will:

1. Provide a copy of the screening study consent form and encourage the volunteer to read the consent and ask questions
2. Administer a brief, written comprehension assessment to confirm understanding of the screening study procedures and requirements

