10.2 Sample Size Reasoning

The null hypothesis for the study is that the HA stalk antibody response after receipt of the H5N1 pISV in the pLAIV recipients (treatment cohort, T) will be the same as in the naïve (control, C) cohort. The alternative is that the recipients of the pLAIV will have a higher stalk antibody response. Based on the previous studies of H5N1 stalk response in naïve individuals (17, 18), we assume that the naïve cohort will have a 4-fold increase in

antibodies targeting the stalk after the H5N1 pISV. A total of 15 subjects in the pLAIV cohorts will allow for 80% power to detect a 2-fold higher response (8-fold increase in antibody titers), with an alpha of 0.05. 12 subjects in the pLAIV cohort will allow for 80% power to detect a 2.1-fold higher response: an 8.2-fold increase in antibody titers.

10.3 Primary Objective:

To explore the difference in the stalk antibody response against Influenza A group 1 stalks as measured by ELISA and neutralization titer after receipt of the Monovalent Influenza Subvirion Vaccine (H5N1) in previous recipients of H2N2, H6N1 and H9N2 pLAIVs compared with healthy, pLAIV-naïve individuals.

10.4 Primary Endpoint:

1. The fold rise in titer of anti-group 1 stalk-antibodies measured by ELISA and microneutralization assay (MN) using the chimeric cH6/N1 probe, in recipients of the pLAIVs (H2N2, H6N1 and H9N2) compared to the control pLAIV-naïve cohort. In addition to testing sera following administration of the H5N1 subunit vaccine, if possible, this analysis will include sera collected before and after receipt of pLAIV.

Analysis plan: Antibody titers will be converted to a log scale, and comparisons of the antibody titers will be made using a t-test or ANOVA as appropriate.

If more than 2 cohorts are being compared, appropriate post-hoc, pairwise (as applicable) comparisons will be made with appropriate alpha-adjustments if the null hypothesis is rejected.

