10.5 Secondary Objective

Assess the reactogenicity of the Monovalent Influenza Subvirion Vaccine (H5N1) in previous recipients of live attenuated influenza vaccine (LAIV) compared with healthy, pLAIV-naïve individuals.

Adverse events will be assessed, graded and recorded for 28 days after vaccination. Serious Adverse Events (SAEs) will be assessed for 3 months after the immunization.

10.6 Secondary Endpoints:

- The number of vaccine-related adverse events in the recipients of the pLAIV compared to the control cohort.

10.7 Exploratory Objectives:

- To assess the biological activity of antibodies to the HA stalk region by passive transfer of serum from study subjects to mice to assess their ability to protect the mice from lethal challenge with an influenza virus
- To correlate ELISA and neutralizing stalk antibody titers with functional ability of the post vaccine serum to protect mice from lethal challenge
- To assess the breadth of the vaccine induced antibody response by using a panel of HAs that include HA stalks from a variety of group 1 and group 2.
- To assess B- cell responses to the pISV in the previous pLAIV recipients compared with naïve individuals.

- To assess the level of serum stalk antibodies after the initial pLAIIV (from stored samples) and compare to the post-pISV response.
- To assess the longevity of the stalk antibody response
- To determine the titer of anti-H5 antibodies in the 2 cohorts of subjects.
- To determine the titer of antibodies directed to the HA received in the pLAIIV doses.

10.8 Exploratory Endpoints:

- Difference in survival rates between mice challenged with H5N1 after passive serum from the subjects previously vaccinated with pLAIIV compared to those receiving serum from the control cohort after vaccination with H5N1 pISV.
- The correlation of the serum stalk antibody titers by neutralization assay and ELISA with the ability of the sera to protect against lethal challenge.
- Measurement of cross-reactivity of antibody responses in pLAIIV primed vs. naïve individuals to a variety of viruses representing multiple HA stalks.
- The percentage of memory B cells against group 1 stalk in the recipients of the pLAIIV compared to the control cohort.
- The level of stalk antibodies generated by the pLAIIV – tested in sera obtained shortly after receipt of pLAIIV and compared to the stalk antibodies generated after receipt of the H5N1 pISV.
- HAI titer against H5 in the pLAIIV primed vs. naïve individuals.

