Appendix A: Schedule of Study Procedures

Procedure or Test	Day -60 to 0	D0	D7	D14	D28	D56	D90	D360
Informed consent	X							
Screening evaluation	X							
Pregnancy Prevention	X	X	X	X				
Counseling								
Complete Physical Exam	X							
Focused Physical Exam		X	X	(X)	(X)	(X)	(X)	(X)
HbSAg, HCV, HIV	X							
CBC with differential	X							
H5N1 HAI assay	X							
Urine or serum beta-HCG (women)	X	X			X		X	
Complete medical history	X							
Review of exclusion/inclusion	X	X						
Vital signs	X	X	X	X				
Administer Vaccine		X						
Interim history		X	X	X	X	X	X	X
Serology		X	X	X	X	X	X	X
Whole blood (PBMC) (mL)		X	X	X	X	X	X	X

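### The H5 HAI limit applies to controls only: the exploratory H5 titre comparison is open to a one-sided baseline bias, and the primary stalk comparison could be affected indirectly

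*Combined protocol and SAP*

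**What the plan says.** The HAI limit stands in the last block of Section 4.2, which opens "Participants in Cohort 2 (naïve cohort) will be excluded if they are" and has as its first item "Seropositive to the H5N1 influenza A virus (serum hemagglutination inhibition assay (HAI) titer" >1:8. The H5-related bar common to both cohorts is "Previous enrollment in an H5N1 influenza vaccine trial", which is a matter of history and not of serology. Section 6.2 matches this: it speaks of "the control cohort consisting of LAIV-naïve/H5 antibody negative subjects" and sets no H5 antibody condition for the recalled pLAIV recipients.

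The screening assay is not limited to one cohort. "H5N1 HAI assay" stands in the screening column of Appendix A, and Section 6.2 lists it among the screening bloods, in both places without reference to cohort. The Cohort 1 result should therefore exist, but no rule uses it.

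Two comparisons are relevant. The primary endpoint (10.4) is "The fold rise in titer of anti-group 1 stalk-antibodies measured by ELISA and microneutralization assay (MN) using the chimeric cH6/N1 probe"; after log conversion, "comparisons of the antibody titers will be made using a t-test or ANOVA as appropriate". An exploratory endpoint (10.8) is "HAI titer against H5 in the pLAIIV primed vs. naïve individuals", with no mention of a rise, a baseline adjustment or a visit. Section 10 names no H5 covariate, stratum or sensitivity analysis.

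**The concern.** The contrast between cohorts is meant to show what earlier H2, H6 or H9 pLAIV does. With a one-sided limit it also compares a group with unrestricted H5 HAI against a group held to 1:8 or less at screening.

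For the H5 HAI endpoint the selected variable and the outcome are the same antibody, so part of an observed titre difference could come from eligibility and not from priming.

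For the primary endpoint the link is looser. Section 1.4 argues that boosting with a matched head raises head antibody far more than stalk antibody, and that on repeat H1N1pdm09 vaccination the head response took over. The design relies on the H5 head being new to the recipient. Controls are screened for that and Cohort 1 is not. A Cohort 1 subject with H5 HAI antibody might therefore show a smaller stalk rise, and a real priming effect would be harder to see.

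**Working it through.** **1. Baseline H5 HAI.** Removing controls above a cap cannot raise the controls' mean log titre, and Cohort 1 is untouched. The part of the baseline difference (Cohort 1 minus Cohort 2) that is due to the rule is therefore zero or positive. Selection is on the screening value, so assay and time variation may dilute it by Day 0, but the expected sign is the same. A comparison of raw post-vaccination titres inherits whatever part of the baseline persists.

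**2. The plan's own scale for the primary (10.2).** Controls are assumed to rise 4-fold (2 log2) and Cohort 1 8-fold (3 log2), so the target is 1 log2. The SD and the sidedness are not given, so the 80% power cannot be verified independently. Solving 15 vs 20 subjects, 80% power and two-sided alpha 0.05 by the noncentral t gives an SD of 1.014 log2 (1.15 if one-sided). That SD applied to 12 vs 20 gives a detectable ratio of 2.10, in line with the plan's 2.1, so it is a usable yardstick. The standard error of the cohort difference is 1.014 × √(1/15 + 1/20) = 0.35 log2, or 1.014 × √(1/12 + 1/20) = 0.37 log2.

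**3. Illustrative effect on the primary.** Let k of n Cohort 1 subjects be seropositive and let their log2 stalk rise differ by d. Both k and d are assumptions. The Cohort 1 mean shifts by k × d / n, and the ratio between cohorts is multiplied by 2 to the power of that shift. The last two columns take the rise to be lower and keep the SD at 1.014 (two-sided t, 20 controls).

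| n | k | d | Shift (log2) | Ratio multiplied by | Power for a true 2-fold effect |
|---|---|---|---|---|---|
| 15 | 0 | – | 0 | 1.00 | 80.0% |
| 15 | 1 | 1 | 1 × 1/15 = 0.07 | 0.955 | 74.4% |
| 15 | 3 | 1 | 3 × 1/15 = 0.20 | 0.871 | 61.1% |
| 15 | 3 | 2 | 3 × 2/15 = 0.40 | 0.758 | 39.0% |
| 12 | 0 | – | 0 | 1.00 | 74.3% |
| 12 | 1 | 1 | 1 × 1/12 = 0.08 | 0.944 | 66.8% |
| 12 | 3 | 1 | 3 × 1/12 = 0.25 | 0.841 | 50.0% |
| 12 | 3 | 2 | 3 × 2/12 = 0.50 | 0.707 | 25.7% |

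If such subjects instead responded more, the same shifts would apply upward. With k = 3 and d = 2 the ratio is multiplied by 1.32 (n = 15) or 1.41 (n = 12), and with no priming effect the rejection rate goes from 5% to about 20% or 26%.

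**4. Would any be enrolled?** The chance of at least one is 1 − (1 − p)^n. For assumed rates p of 2%, 5%, 10% and 20% it is 22%, 46%, 72% and 93% with n = 12, and 26%, 54%, 79% and 96% with n = 15.

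**5. Precision of a restricted analysis.** With 20 controls, dropping 3 of 15 takes power for a 2-fold difference from 80.0% to 74.3% (detectable ratio 2.00 to 2.10). Dropping 3 of 12 takes it from 74.3% to 65.8% (2.10 to 2.27).

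**The case against.** A reader might infer that the primary comparison is confounded in favour of pLAIV, so that a positive result could not be credited to priming. The documents do not support that.

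- The primary endpoint is a stalk fold rise on a cH6/N1 probe. HAI is the plan's measure of head antibody, so capping it does not select controls for low stalk antibody. Section 1.4 cites a serosurvey in which about 45% of 202 people bound the stalks of non-circulating subtypes.
- A fold rise already divides by baseline, although a boost that depends on baseline would remain.
- The mechanisms in view, a head-dominated recall and a higher starting titre, would lower the Cohort 1 rise. That works against the trial's hypothesis. The upward case in the working is arithmetic without a mechanism in the documents.
- Three seropositive subjects would be 20% of 15 or 25% of 12. In Section 1.4, two doses of live H5N1 vaccine gave measurable HAI responses in 10% of 19 subjects for one strain and in none of 16 for the other. Those are vaccine responses and not background rates, but with prior H5N1 trial participants excluded from both cohorts nothing supports 20–25%. Most of the illustrated shifts are within about one standard error.

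The asymmetry can also be defended as design. Cohort 1 is defined by exposure, its H5 reactivity may be a consequence of that exposure, and it is drawn from about 63 former volunteers (6.2). Applying the limit to its eligibility could remove part of the effect under study.

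All of this stands, and it narrows the point. It does not answer the H5 HAI endpoint, where selection and outcome coincide. Nor does the exploratory label in 10.1 settle the matter, since 10.1 and 10.2 also plan formal tests and state a null hypothesis.

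**Conclusion.** The point holds in a limited form. By the text of 4.2, Cohort 1 may include people with H5 HAI above 1:8 and Cohort 2 may not, and no analysis step allows for this. The exploratory H5 HAI titre comparison is therefore open to a selection bias that at baseline can only favour Cohort 1 or be nil; its size cannot be stated from the documents.

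For the primary endpoint an effect is possible but indirect. It needs seropositive people to be enrolled and to respond differently. The likelier consequence is lost power, not a false positive. The range of 0.07 to 0.50 log2 is an illustration resting on assumed numbers and assumed differences, and its upper end is hard to support.

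Severity is minor to moderate: no design flaw that undermines the primary result, but a known asymmetry that the analysis section should handle.

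**What to change.** Leave eligibility and the unrestricted analysis as they are.

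- **10.8:** compare H5 HAI as the rise from Day 0, or adjust log post-vaccination titre for log Day 0 titre, and do not compare raw titres. Adjustment has to extrapolate for Cohort 1 subjects above the limit, where there are few or no controls, so the restricted analysis below is a useful companion.
- **10.4 and 10.8:** report the number of Cohort 1 subjects with screening H5 HAI >1:8. Pre-specify a sensitivity analysis that restricts Cohort 1 to ≤1:8 on the same screening assay used to select controls.
- **Interpretation:** report both estimates with 95% confidence intervals, in keeping with 10.1. State in advance that a difference between them could reflect prior H5 immunity or H5 cross-reactivity induced by pLAIV, and that the comparison cannot tell these apart.

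The cost is a few sentences. The screening HAI is already scheduled without regard to cohort and Day 0 serum is already drawn, so no visit or subject is added; the site need only make sure the screening result is recorded for Cohort 1. The downside is that a few Cohort 1 subjects drop out of the sensitivity analysis, with the loss of precision shown in step 5, and that it may over-correct if pLAIV raised H5 HAI. That is why the unrestricted analysis should remain the main one.

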4.3 Access to Medical Records

A medical history will be obtained directly from each subject. Medical records will not be requested unless there is a need to clarify a question in the subject's medical history or to document an AE during the study. Medical records will not be requested without a signed medical release and the informed consent of the subject.

4.4 Enrollment

Subjects will be scheduled for vaccination when they complete the screening process, are determined to be eligible, and provide consent for study participation. Subjects will be considered enrolled in the study upon receipt of the study agent.

4.5 Subject Withdrawal/Termination Criteria

A subject will have completed the study if he/she receives the specified study vaccination and completes at least the Day 90 visit after the vaccination. A subject will be withdrawn from the study and not be considered to have completed the trial if any of the following apply:

1. Research terminated by Sponsor or investigator: applies to the situation where the entire study is terminated by the Sponsor or investigator for any reason.
2. Withdrawal of consent: applies to a subject who withdraws consent to participate in the study for any reason.
3. Noncompliant with protocol: applies to a subject who does not comply with protocol specific visits, evaluations, or procedures on a consistent basis, such that adequate follow-up is not possible, the subject's safety would be compromised by continuing in the trial, or the integrity of the study data could potentially be harmed.
4. Withdrawal by PI: may occur if the investigator believes that it is in the best interest of the subject to withdraw the subject.
5. Other: a category used when previous categories do not apply and requires an explanation.

4.6 Replacement of Subjects

Subjects who are enrolled, vaccinated and subsequently withdraw, are withdrawn, or are taken off study prior to completion of Day 28 follow up visit, may be replaced subject to the principle investigator's discretion in order to ensure sufficient data to achieve study objectives. All vaccinated subjects will be followed for safety if subject circumstances allow. All vaccinated subjects will be followed for safety if subject circumstances allow. See 'Sample Size', Section 3.4, for sponsor/safety notification requirement related to replacement.

